10.5 Primary Endpoints

Time to an intubation event in hours from the start of the study drug infusion or overall duration of mechanical ventilation will represent the primary clinical endpoint. The number of patients starting intubation over time will be displayed in the form of survival curves using the Kaplan-Meier method and analyzed using a two-sided log-rank test. Statistical significance will be claimed if the computed p-value is equal to or less than 0.05.

Citrulline and arginine plasma levels will represent the primary biochemical endpoint of this study. A 5 mL sample of blood will be obtained for amino acid analysis at hour 0 before study medication is administered, 2 and 12 hours after the bolus and as close as possible to 8 AM on days 2, 4, 6, 8, and 10. Samples will be collected in citrated tubes and placed on ice until they can be centrifuged. Plasma and cellular components will be frozen at -70 °C until batch analysis. Concentrations of citrulline, arginine, and ornithine will be measured in the plasma samples using cation-exchange chromatography with a Beckman 7300 amino acid analyzer or equivalent. The analysis team will provide the means and standard

deviations for citrulline, arginine, and ornithine plasma levels separately for each treatment group. A generalized linear mixed model (GLMM) with appropriate link function (i.e., identity link for continuous outcome) will be used to compare these plasma amino levels across the two intervention groups. The model will examine how the treatment means differ (i.e., main treatment effect), how treatment means change over time (i.e., main time effect), and how differences between treatment means change over time (i.e., treatment-by-time effect).

The primary safety outcome will be worst VDI any time after start of infusion. VDI is a continuous variable calculated by dividing vasopressor index (summation of all pressors) by MAP. VDI will be calculated at baseline (immediately before start of the infusion), 2 hours after completion of the bolus, and every 4 hours during the infusion. Worst VDI will be compared between groups using ANCOVA analysis with the baseline VDI as the covariate.

10.6 Secondary Safety Endpoints

Although VDI will represent the primary outcome for determining safety, other measures will also be employed.

10.6.1 Secondary Clinical Endpoints

All-cause, hospital mortality, defined by whether the patient was discharged from the hospital alive or deceased, will be analyzed via two statistical methods. The proportion of patients who have died by hospital discharge will be analyzed using a Chi-square analysis or Fisher's Exact Test, if needed. In addition, time to death will also be analyzed using a log-rank method of a Kaplan-Meier analysis. ICU length of stay (LOS) will be defined in days as the time from study enrollment to the day ICU discharge orders are written, regardless of when the patient physically leaves the ICU. Comparison will be made between the two groups for total ICU length of stay which will include any days of ICU re-admission prior to hospital discharge. Hospital length of stay will be defined as time from study enrollment to first hospital discharge. We will consider both ICU LOS and hospital LOS as count measure and has the potential to follow a skewed distribution. Initially, we will assess the distributional assumption. We will use a generalized linear model (GLM) to compare the expected ICU LOS and hospital LOS between the two treatment groups (placebo and intravenous citrulline). Specifically, we will use a negative binomial distribution and log-link to account for potential over-dispersion. We will report point estimates for the group mean difference along with a 95% confidence interval. Overall duration of mechanical ventilation will be modeled with zero-inflated Poisson or negative binomial method using consent and post-infusion start time for two separate analysis.

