6.2 Inclusion Criteria

Participant eligibility is determined based on the selection of criteria detailed below:

1. Age 18-65 years.
2. Clinical evidence of COVID-19 (SARS-CoV2) infection, defined as a positive COVID-19 laboratory test plus evidence of an acute hypoxic respiratory illness requiring oxygen.
3. Admitted and transferred to floor without intubation.

6.3 Exclusion Criteria:

Patients meeting any of the following criteria will not be eligible for participation in the study:

1. No consent/inability to obtain consent
2. Patient, surrogate, or physician not committed to full support
3. Malignant or other irreversible condition and estimated 28-day mortality $\geq 50\%$
4. Moribund patient not expected to survive 48 hours (as defined by primary medical team) from start of study infusion
5. End-stage Liver Disease as defined by Child-Pugh Score > 9
6. Currently enrolled in, or participated in another study of an investigational compound within the last 30 days
7. Pregnant female, or female who is breast feeding
8. Allergy to L-citrulline or arginine or any citrulline- or arginine-containing product
9. Patient not otherwise suitable for the study in the opinion of any of the investigators
10. Requirement for intubation and invasive mechanical ventilation before study enrollment

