7.1.4 Mortality, Hospital, and ICU Length of Stay Assessment

Participant survival will be assessed at hospital discharge. ICU length of stay will be the total number of days the participant spends in the ICU from time of enrollment to hospital discharge. Re-admissions to the ICU during the initial hospital stay will be added to the initial ICU length of stay to determine a total number of ICU days. Hospital length of stay will be calculated as the number of days from enrollment to

hospital discharge. Once the patient is discharged from the hospital (to any disposition including home, home with help, rehab, or another hospital) or dies, hospital days will cease. Subsequent re-admissions to the hospital or ICU after hospital discharge will not be added to the hospital or ICU lengths of stay, respectively.

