#### ***Length of ICU Stay***

ICU length of stay (LOS) will be defined in days as the time from study enrollment to the day ICU discharge orders are written, regardless of when the patient physically leaves the ICU. Comparison will be made between the two groups for total ICU length of stay which will include any days of ICU re-admission prior to hospital discharge. We will consider ICU LOS a count measure and has the potential to follow a skewed distribution. Initially, we will assess the distributional assumption. We will use a generalized linear model (GLM) to compare the expected ICU LOS between the two treatment groups (placebo and intravenous citrulline). Specifically, we will use a negative binomial distribution and log-link to account for potential over-dispersion. We will report point estimates for the group mean difference along with a 95% confidence interval.

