### ***Length of Oxygen Therapy in Hours***

### ***Length of Non-invasive Mechanical Ventilation***

We will provide median and range of length of non-invasive mechanical ventilation separately for each treatment group. There is an expectation that some patients will not require mechanical ventilation; therefore, overall duration of mechanical ventilation will be modeled with a zero-inflated Poisson model using consent and post-infusion start time for two separate analysis.

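### If a sizeable share of patients never enter the ICU, the planned negative binomial model overstates the standard error for ICU stay; the plan needs a scoring rule for these patients and a robust standard error.

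*Protocol*

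**What the plan says.** Protocol 10.6.1 treats ICU stay as a count and compares arms by a generalized linear model: "Specifically, we will use a negative binomial distribution and log-link to account for potential over-dispersion". Just before that it promises a check, "Initially, we will assess the distributional assumption", but names no criterion and no alternative model. The result to be reported is a difference in means: "We will report point estimates for the group mean difference along with a 95% confidence interval". SAP, Length of ICU Stay, carries the same plan: "We will consider ICU LOS a count measure and has the potential to follow a skewed distribution" and "We will use a generalized linear model (GLM) to compare the expected ICU LOS between the two treatment groups". Neither document gives the model a separate part for zeros.

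The analysis set is all randomized patients (Protocol 10.1; SAP, Analysis Populations). They enter under the criterion "Admitted and transferred to floor without intubation" (Protocol 6.2).

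Two definitions of ICU stay sit side by side. Protocol 7.1.4 says "ICU length of stay will be the total number of days the participant spends in the ICU from time of enrollment to hospital discharge", which implies 0 for a patient never admitted. Protocol 10.6.1 and the SAP instead measure from enrolment to the day ICU discharge orders are written, and that day does not exist for such a patient. No section states the score.

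For ventilation the plan does foresee zeros: "There is an expectation that some patients will not require mechanical ventilation" (SAP, Length of Non-invasive Mechanical Ventilation), and it uses a zero-inflated model there.

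**The concern.** If an appreciable share of patients stay on the floor, ICU days have a block at 0 and a separate group at several days. A negative binomial distribution has one mean and one dispersion per fit and cannot take that shape. Maximum likelihood raises the dispersion to accommodate the zeros, and the model-based standard error rises with it.

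With treatment as the only term, the fitted group means are the sample means, so the point estimate is not harmed. The confidence interval and p-value are. The error is conservative: a real reduction in ICU days, including one obtained by keeping patients out of the ICU, could be reported as no difference. The SAP adjusts the secondary endpoints by Hochberg, which steps down from the largest p-value, so a needlessly large p-value here can also tighten the threshold for the others.

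The missing score matters too. The SAP imputes only biochemical outcomes, so never-admitted patients could be dropped as missing, which would leave a comparison among ICU patients only.

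**Working it through.** **The plan's own figures.** The documents state no ICU admission rate, ICU-stay distribution, target effect or power for this endpoint. The nearest stated figure is 81% power for the log-rank test with 60 patients and hazard ratio 0.46 (Protocol 10.4). It reproduces. Freedman: (1.960 + 0.878)² × (1.46/0.54)² = 8.05 × 7.31 ≈ 59 events. Schoenfeld: 4 × 8.05 / (ln 0.46)² = 32.2/0.603, or 54 events.

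**Inputs.** 30 per arm (66 randomized less 10%, Protocol 10.4) and two-sided 5% come from the documents. Assumed: the share p ever admitted, and ICU days among those admitted as rounded gamma with mean 10. Shapes 6-7 follow the ventilation figures in Protocol 3.4 (median 10 days, IQR 7-12), used as a proxy; shape 2 or 2.5 is a more skewed case.

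**Mechanism by hand** (p = 0.5 in both arms, mean 10, shape 2.5, rounding to whole days ignored):
- Overall mean μ = 0.5 × 10 = 5. Squared coefficient of variation = (1 + 1/2.5)/0.5 − 1 = 1.8.
- True SD of the log mean ratio ≈ √(2 × 1.8/30) = 0.346 (simulated 0.352).
- The dispersion that would reproduce this variance is 1.8 − 1/5 = 1.6. It predicts a zero share of (1 + 1.6 × 5)^(−1/1.6) = 25%, against 50% in the data.
- The fitted dispersion is 3.65, which predicts (1 + 3.65 × 5)^(−1/3.65) = 44% zeros.
- Model-based SE = √(2 × (1/5 + 3.65)/30) = 0.507 (simulated 0.511).
- Simulated ratio 0.511/0.352 = 1.45. The nominal cut-off of 1.96 acts like 1.96 × 1.45 = 2.84. Simulated rejection under no effect: 1.2%.
- If everyone is admitted, the squared coefficient of variation is 0.4. The dispersion that matches the variance is 0.4 − 0.1 = 0.3, and 0.1 + 0.3 returns 0.4, so the excess disappears.

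**Simulation, no treatment effect** (30 per arm; shape 7 for the first three rows, shape 6 for the last two):

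| Admitted | Model SE / true SD | NB test rejects | 95% CI coverage | NB with sandwich SE rejects | Wilcoxon rejects |
|---|---|---|---|---|---|
| 30% | 1.59 | 0.6% | 99.4% | 4.0% | 5.3% |
| 50% | 1.59 | 0.2% | 99.8% | 5.0% | 5.4% |
| 75% | 1.41 | 0.9% | 99.1% | 4.6% | 4.7% |
| 90% | 1.15 | 3.6% | 96.3% | 5.5% | 5.1% |
| 100% | 0.94 | 6.9% | 93.3% | 6.0% | 5.2% |

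Over all shapes at 30-75% admitted, the SE ratio is 1.2-1.6, rejection 0.2-2.2% and coverage 98-99.8%.

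**Simulation, power** (30 per arm, shape 7 unless noted, days given as placebo → citrulline):

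| Effect | NB, model SE | NB, sandwich SE | Wilcoxon | NB model / Wilcoxon |
|---|---|---|---|---|
| Admission 50% → 25% | 13.7% | 40.3% | 49.6% | 0.28 |
| Admission 50% → 17% | 36.2% | 64.7% | 77.0% | 0.47 |
| Admission 60% → 30% | 18.7% | 50.8% | 60.9% | 0.31 |
| Admission 75% → 50% | 11.8% | 35.7% | 39.9% | 0.30 |
| Admission 75% → 40% | 30.1% | 62.2% | 68.7% | 0.44 |
| 50% → 25% and 10 → 8 days | 29.1% | 64.4% | 61.3% | 0.48 |
| 75% → 50% and 10 → 8 days | 41.4% | 73.9% | 72.4% | 0.57 |
| 75% → 50% and 10 → 6 days | 85.1% | 97.4% | 94.4% | 0.90 |
| 50% admitted, 10 → 6 days | 9.5% | 40.5% | 20.3% | 0.47 |
| 75% admitted, 10 → 6 days | 52.9% | 76.4% | 69.1% | 0.77 |
| Same, shape 2 | 35.8% | 50.5% | 27.1% | 1.32 |

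Over all scenarios the last column runs 0.28-0.53 for admission-only effects with 30-86% of placebo patients admitted, 0.55-0.72 for admission-only effects with 90-95% admitted, 0.48-0.97 when stay also shortens, and 0.47-1.39 for stay-only effects. Results at 33 per arm are similar. These are powers at the unadjusted 5% level; Hochberg would lower them.

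**The case against.** The zero share is unknown, and one design assumption points to a small one: 81% power with 60 patients needs 54-59 intubations, so nearly everyone. Protocol 5.1.1 also speaks of delivery to the ICU. If almost all patients reach the ICU, the problem largely goes away. That stands, and it makes the finding conditional. Against it, enrolment is on the floor, Protocol 5.1.2 reserves ICU monitoring for patients who become critically ill, and the SAP expects some patients never to be ventilated.

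The plan also promises a distribution check. That softens the point, but with no criterion or fallback the replacement would be chosen after seeing the data.

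A reader might infer that the planned model has only a quarter to half of a rank test's power in general. The documents do not support this: it needs a substantial never-admitted share and an effect almost wholly on admission, and neither is stated. With a stay-only effect the planned model can do better than the rank test.

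A reader might also infer that a rank test should replace the model. The plan compares expected ICU stay and reports a mean difference, and a rank test addresses a different hypothesis. The demonstrated fault is the variance, and a robust variance repairs it without changing what is estimated.

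**Conclusion.** The concern holds in conditional form. If about 30-75% of patients are ever admitted to the ICU and the rest score 0, the model-based standard error is about 1.2-1.6 times too large, and the nominal 5% test runs at about 0.2-2%. At 90% admitted the excess is about 1.10-1.15; at 100% there is none.

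The loss of power against a rank test is large (ratio about 0.3-0.5) only for an effect mainly on admission. The ratio is about 0.5-1 when stay is also shortened. It has no fixed direction when only stay is shortened.

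These sizes rest on an assumed admission rate, an assumed gamma shape, and the zero score that Protocol 7.1.4 implies but no section states. Hospital stay, which uses the same model, has no block of zeros. The endpoint is secondary and the error is conservative; the primary log-rank analysis is not touched.

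**What to change.** In Protocol 10.6.1 and SAP, Length of ICU Stay:

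1. State that a randomized patient never admitted to the ICU scores 0 ICU days and is included, and align the definition with Protocol 7.1.4.
2. Keep the planned mean comparison, but take its p-value and 95% confidence interval from a sandwich (robust) or bootstrap standard error instead of the model-based one.
3. Optionally, add a Wilcoxon test stratified by age group (van Elteren) as a supportive analysis, labelled as such because it can disagree with the mean comparison.

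The cost is a few lines of SAP text and code, with no new data. The robust standard error can be mildly anti-conservative at 30 per arm (about 5-6%). If every patient is admitted it gives up a little power: 79.5% against 82.0% for 10 → 6 days at shape 2. In every unequal-arm case simulated with some patients never admitted, it had more power than the planned test.

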10.7 Interim Analyses

No formal interim analyses for efficacy will be done in this phase 2 study. A safety analysis looking at VDI and hypotension will be undertaken after the first 20 patients have completed enrollment to ensure that citrulline administration is not causing hypotension.

11.0 ETHICS

11.1 Ethical Conduct of the Trial

This study will be conducted with the highest respect for individual participants according to the protocol, the World Medical Association Declaration of Helsinki, the Guideline for Good Clinical Practice, and the

Belmont Report. Furthermore, the study will be conducted in accordance with the Common Rule (45 CFR 46), as guided by the Department of Health and Human Services via the Office of Human Research Protections.

11.2 Institutional Review Board

The investigator and sponsor will submit all relevant documents to the IRB for the protocol's review and approval. The study, protocol, informed consent form, investigator's brochure, and any proposed advertising or recruitment materials must be approved by the local IRB prior to commencing the study. Written approval by the IRB of the protocol and participant informed consent document must be obtained prior to enrollment of any participants. If any member of the IRB has direct participation in this trial, he or she must refrain from any IRB discussions or votes pertaining to this study.

Sites must adhere to all requirements stipulated by their respective IRBs. This may include notification to the IRB regarding: protocol amendments, updates to the informed consent document, recruitment materials, local safety reporting requirements, and closure of the study.

11.3 Participant Information, Informed Consent, and Participant Authorization

All consent for participation in this study must occur via written consent documents, which should contain the elements of informed consent as required by 45 CFR 46 and the Declaration of Helsinki. The informed consent document will describe the planned and permitted uses, transfers, and disclosures of the participant's personal and personal health information for purposes of conducting the study.

The investigator is responsible for the preparation, content, and submission to the IRB approval of the informed consent form. The informed consent form and any participant information sheet must be approved by the IRB prior to use.

The participant, or his or her legally authorized representative, must be presented with an informed consent document written in their native language and given ample opportunity to: 1) inquire about details of the study, and 2) decide whether or not to participate in the study. If the participant or legally authorized representative agrees to participate in the study, the informed consent form must be signed and dated by the participant or legally authorized representative prior to the participant being enrolled in the study. The investigator must document the date the ICF is signed in the participant's medical record. The investigator must also sign and date the informed consent form at the time of consent and prior to the participant being entered into the study.

Once signed by both the participant and investigator, a copy of the informed consent document will be given to the participant (or legally authorized representative). The original informed consent document will be stored in the investigator's site file. All revised informed consent forms must be reviewed and signed in the same manner as the original informed consent. The date the revised consent was obtained should be recorded in the participant's medical record and the participant should receive a copy of the revised ICF. If surrogate consent was utilized for initial consent, the participant should be "re-consented" by signing the original ICF when he or she regains the capacity to consent. The participant should date this "reconsent" with the actual date of reconsenting and not with the date of the original consent signing by the legally authorized representative.

11.4 Data and Safety Monitoring Plan

The Principal Investigator, along with the Chief Medical Officer at Asklepion (safety officer) will be responsible for overseeing the safety of this trial. There is no formal data safety monitoring board planned for this trial. Laboratory and clinical data will be reviewed daily for adverse events by the safety officer. In addition, the safety officer will be available at any time for questions from the co-investigators at UAMS, who will be monitoring the patients continuously for potential adverse events. There will be no interim analyses of the data for efficacy with the exception of an initial independent PK evaluation (separate from study team) of first 2 subjects for all the time points to ensure steady state concentration is being attained. The safety officer will be available to review serious adverse events in a timely manner. Furthermore, in cases of serious adverse events or significant hypotension, the safety officer can request unblinding of the treatment arm and/or an urgent amino acid analysis to better guide decision-making. The safety officer will have the ability to pause the trial in agreement with the co-investigators to enable investigation of possible safety issues and/or suggest changes to the design of the study to abrogate any safety issues, including discontinuation of the initial bolus should it result in unacceptable hypotension.

11.5 Potential Risks

All patients will reside in a hospital unit or intensive care unit environment, where close monitoring can be achieved and rapid response to any potential adverse event, including hypotension, will occur. Should a patient improve and be weaned off all oxygen support prior to completion of the study drug infusion, the study drug will be stopped but data will continue to be collected. Patients will be monitored by the bedside or ICU nurse for the duration of the infusion per standard unit protocol. The investigator and/or coordinator will be available by pager 24 hours a day 7 days a week to answer any questions that the bedside nurse has.

All patients will have blood drawn for research purposes. The risks of drawing blood are uncommon and may include bleeding and bruising. Commonly, having blood drawn is painful, and rarely can lead to infection at the site of the blood draw. It is anticipated that most of the blood obtained for research purposes will be obtained through existing intravenous peripheral, central, or arterial catheters since these patients routinely have such catheters while in the intensive care units. The amount of blood drawn is minimal and represents a small percentage of the amount of blood taken during a standard hospital or ICU stay and will not represent a significant risk to the patient.

The risks of citrulline are theoretical. In previous studies enrolling hundreds of humans, no serious adverse events have been attributed to either oral or intravenous citrulline. Citrulline may increase NO production and exacerbate hypotension. Arginine, a product of citrulline via the urea cycle, has been reported to exacerbate hypotension. The blood pressure of every participant in this study will be monitored closely throughout the study and especially during the infusion. As these patients will be cared for in a hospital unit or ICU, blood pressure measurements will be taken per hospital unit or ICU protocol. Hypotension, as measured by vasopressor dependency index (VDI) represents an *a priori* endpoint of the study. VDI will be calculated 2 hours after the bolus and daily. Any worsening of VDI by 33% or more will prompt review by the safety monitor. Although it is likely to reduce organ dysfunction by attenuating inflammation and oxidative stress, daily labs will be monitored for adverse events on organ functioning. The citrulline will be administered in a small volume of 5% dextrose water (30 mL bolus followed by ~15 mL/hr). This small amount of dextrose should not dramatically increase blood sugar levels in these patients and as such, should pose minimal risk. Furthermore, any event which the investigator or primary team is concerned may be related to study drug administration will be reported as an adverse event. Participants will be monitored for any signs of allergic reaction, including new wheezing, itching and/or rash. Blood pressure, which might fall during severe allergic reactions such as anaphylaxis, will be closely monitored in the hospital or ICU setting with treatment available as needed.

The placebo will be a small volume of 5% dextrose water (30 mL bolus followed by ~15 mL/hr). Although administration of dextrose in theory could raise blood sugar levels, the small volume will result in little dextrose being administered which should not significantly increase blood sugar levels in these patients and as such, should pose minimal risk. In addition, blood sugar levels are routinely measured and monitored closely as part of routine care in intensive care unit patients, especially those with severe sepsis.

Another potential risk to participants is the breach of confidentiality including information from their medical record. There are many safeguards in place to prevent the release of information from this study. All data for this study will be stored in a password-protected, HIPAA security compliant computer database. Initially it will be recorded on case report forms which will be stored in a locked office that only the study personnel have access to. This is especially true since some genetic tests will be run utilizing these samples. All samples obtained for this study will be assigned a code which will not identify the subject. The only key to the code will be in the password-protected computer database. [name], and the study co-investigator will have access to the code and information that identifies a participant as a being in this study. The results of analyses run on those samples will not be reported to the participant or primary study team. No one else, including relatives, doctors, employers, or insurance companies will be allowed to view the test results. The codes linking the patients with their data will be destroyed after all participants have completed the study and the data has been through quality assurance processes. Informed consent documents will not bear the study identification number so that once the code is destroyed; there will be no possible way the results could be traced back to the individual.

